7.11 Safety Analysis

All safety analyses will be performed using the safety analysis set.

7.11.1 Adverse Events

An AE is defined as any untoward medical occurrence in a clinical investigation subject administered a drug. All AEs will be coded by system organ class (SOC) and preferred term (PT) using the Medical Dictionary for Regulatory Agencies (MedDRA 20.0).

A treatment-emergent adverse event (TEAE) will be defined as an AE that starts or worsens on or after Study Day 1 (defined as day first dosed), and no more than 30 days after the last dose of study drug (onset date – last date of dose +1≤30).

In an TEAE overview table, the number and percentage of subjects who experience AEs, TEAEs, TEAEs by severity and relationship, SAEs, discontinued from study treatment due to an AEs, death will be summarized by dose groups and overall.

In addition, the number and percentage of subjects with AEs will be summarized in several different tables:

- All TEAEs by system organ class (SOC) and preferred term (PT).
- TEAE by PT.
- Most frequent TEAEs (>5% or >2 subjects in any dose group).
- Most frequent non-serious TEAEs (>5% or >2 subjects in any dose group).
- Drug-related TEAEs by SOC and PT.
- Relationship to study drug for all TEAEs by SOC and PT (related vs not related).
- All SAEs by SOC and PT.
- Severity of all TEAEs by SOC and PT (mild, moderate, or severe).
- Severity of drug-related TEAEs by SOC and PT (mild, moderate, or severe).

A subject with 2 or more AEs within the same level of the MedDRA term will be counted only once in that level using the most extreme incident (most severe for the severity tables and related for the relationship to study drug tables).

Additionally, treatment-emergent serious adverse events, deaths, and TEAEs resulting in premature discontinuation from study drug will be listed.

A pretreatment event (PTE) is defined as any untoward medical occurrence in a clinical investigation subject who has signed informed consent to participate in a study but prior to administration of any study drug.

Data listings will be provided for all AEs including PTEs, TEAEs, AEs leading to study drug discontinuation, and SAEs.

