10.2.1.2 PTE and AE Reporting

At each study visit, the investigator will assess whether any subjective AEs have occurred. A neutral question, such as "How have you been feeling since your last visit?" may be asked. Subjects may report AEs occurring at any other time during the study. Subjects experiencing a serious PTE must be monitored until the symptoms subside and any clinically relevant changes in laboratory values have returned to baseline or there is a satisfactory explanation for the change. Non-serious PTEs, related or unrelated to the study procedure, need not to be followed-up for the purposes of the protocol.

All subjects experiencing AEs, whether considered associated with the use of the study medication or not, must be monitored until the symptoms subside and any clinically relevant changes in laboratory values have returned to baseline or until there is a satisfactory explanation for the changes observed. All PTEs and AEs will be documented in the PTE/AE page of the eCRF, whether or not the investigator concludes that the event is related to the drug treatment. The following information will be documented for each event:

1. Event term.
2. Start and stop date and time.
3. Frequency.
4. Severity.
5. Investigator's opinion of the causal relationship between the event and administration of study medication(s) (related or not related) (not completed for PTEs).
6. Investigator's opinion of the causal relationship to study procedure(s), including the details of the suspected procedure.

7. Action concerning study medication (not applicable for PTEs).
8. Outcome of event.
9. Seriousness.

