10.2.2 Collection and Reporting of SAEs

When an SAE occurs through the AE collection period it should be reported according to the following procedure:

A Takeda SAE form must be completed, in English, and signed by the investigator immediately or within 24 hours of first onset or notification of the event. The information should be completed as fully as possible but contain, at a minimum:

- A short description of the event and the reason why the event is categorized as serious.
- Subject identification number.
- Investigator's name.
- Name of the study medication(s).
- Causality assessment.

The SAE form should be transmitted within 24 hours to the attention of the contact listed in Section 1.0.

Any SAE spontaneously reported to the investigator following the AE collection period should be reported to the sponsor if considered related to study participation.

Reporting of Serious PTEs will follow the procedure described for SAEs.

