12.1 CRFs (Electronic and Paper)

Completed eCRFs are required for each subject who signs an informed consent.

The sponsor or its designee will supply investigative sites with access to eCRFs. The sponsor will make arrangements to train appropriate site staff in the use of the eCRF. These forms are used to transmit the information collected in the performance of this study to the sponsor and regulatory authorities. eCRFs must be completed in English.

After completion of the entry process, computer logic checks will be run to identify items, such as inconsistent dates, missing data, and questionable values. Queries may be issued by Takeda personnel (or designees) and will be answered by the site.

The principal investigator must review the eCRFs for completeness and accuracy and must e-sign the appropriate eCRFs as indicated. Furthermore, the investigator must retain full responsibility for the accuracy and authenticity of all data entered on the eCRFs.

After the lock of the clinical study database, any change of, modification of or addition to the data on the eCRF should be made by the investigator with use of change and modification records of the eCRFs. The principal investigator must review the data change for completeness and accuracy, and must sign and date.

eCRFs will be reviewed for completeness and acceptability at the study site during periodic visits by study monitors. The sponsor or its designee will be permitted to review the subject's medical and hospital records pertinent to the study to ensure accuracy of the eCRFs. The completed eCRFs are the sole property of the sponsor and should not be made available in any form to third parties, except for authorized representatives of appropriate governmental health or regulatory authorities, without written permission of the sponsor.

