13.1.4 Safety Analysis

All AEs will be coded by system organ class (SOC) and preferred term (PT) using the MedDRA. Treatment-emergent adverse events (TEAEs) with onset occurring within 30 days (onset date – last date of dose +1≤30) after study drug administration will be included in the summary tables. All AEs will be in the listings. TEAEs will be summarized by SOC and PT. The following summary tables will be included in the report: summary of TEAEs and drug-related AEs, relationship of AEs to study drug (related vs not related), severity of AEs, and related AEs. Data listings will be provided for all AEs including PTEs, TEAEs, AEs leading to study drug discontinuation, and SAEs.

Baseline, postdose, and change from baseline to postdose laboratory values will be summarized using descriptive statistics for each dose group. A table with predefined criteria for markedly abnormal values for laboratory variables will be presented. All clinical laboratory data will be listed.

Vital signs will be summarized for each dose group by presenting descriptive statistics for baseline, postdose, and change from baseline to postdose values. Vital signs that meet predefined markedly abnormal criteria will be presented. All vital sign data will be provided in the data listings.

Shift tables for ECG evaluation will be provided overall. All ECG data will be listed in the data listings.

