- (l) Pretreatment AEs will be captured immediately following the signing of the informed consent at Screening and prior to study drug administration. Follow-up site or telephone visit will be made 5-10 days after last dose of study drug to inquire about any TEAE or SAEs, and concomitant medications taken since final dose. Any TEAE/SAE spontaneously reported within 30 days postdose will be included within the database as a TEAE.

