7.2.5 Definition of Study Days

Study day will be calculated relative to the date of the first dose of study drug in the study. The study day prior to the first dose of study drug will be calculated as:

Date of assessment/event – date of first dose of study drug

The study day on or after the first dose of study drug will be calculated as:

Date of assessment/event – date of first dose of study drug + 1.

AEs that start more than 30 days after the last dose of study drug will be listed, but excluded from the summaries and analyses.

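### Do the one-day mismatch in the TEAE window and the differing late-SAE passages call for a change?

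*SAP*

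**What the plan says.** **The window.** SAP 7.11.1 defines a TEAE as an event that starts or worsens from Study Day 1 and "no more than 30 days after the last dose of study drug (onset date – last date of dose +1≤30". Protocol 13.1.4 uses the same formula with different words: "onset occurring within 30 days (onset date – last date of dose +1≤30) after study drug administration". SAP 7.2.5 adds an exclusion: "AEs that start more than 30 days after the last dose of study drug will be listed, but excluded from the summaries and analyses". The same section numbers days from dosing onward as "Date of assessment/event – date of first dose of study drug + 1", so the dosing day is Study Day 1.

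**Late serious events.** Protocol 10.2.2 says: "Any SAE spontaneously reported to the investigator following the AE collection period should be reported to the sponsor if considered related to study participation". Appendix A footnote (l) says: "Any TEAE/SAE spontaneously reported within 30 days postdose will be included within the database as a TEAE". Protocol 10.2.1.2 requires every event to be "documented in the PTE/AE page of the eCRF, whether or not the investigator concludes that the event is related to the drug treatment", and Protocol 12.1 says of the eCRFs: "These forms are used to transmit the information collected in the performance of this study to the sponsor and regulatory authorities". Appendix B, item 12, asks the investigator to notify the sponsor of an SAE within 24 hours and sets no condition on relatedness.

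**End of collection.** Protocol 10.2.1.1 ends routine AE collection at the final visit or early termination. Its next sentence provides a contact 5 to 10 days after dosing to collect further AEs. Appendix A footnote (b) describes routine collection as running through that contact.

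**The concern.** The words and the formula in SAP 7.11.1 are meant to be the same rule, and they are not. An onset 30 days after the dose is a TEAE by the words, is not one by the formula, and is not removed by SAP 7.2.5. TEAE status feeds nearly every adverse event table, and safety is the secondary objective, so a reader could fear that tables depend on which half of the sentence the programmer follows.

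The late-SAE passages raise a similar worry. Protocol 10.2.2 ties reporting to relatedness, while footnote (l) does not. A site that read only 10.2.2 might not send an unrelated SAE that footnote (l) expects in the database. The table of all SAEs by system organ class and preferred term could then miss an event. The two descriptions of where routine AE collection ends leave the start of that period open.

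**Working it through.** **Inputs.** The trial gives one dose on Day 1 (Protocol 2.0), so first and last dose dates coincide. Let d = onset date minus dose date. The rules are:

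- formula (SAP 7.11.1, Protocol 13.1.4): d + 1 ≤ 30, so d ≤ 29;
- words (SAP 7.11.1): d ≤ 30;
- exclusion (SAP 7.2.5): d > 30;
- Study Day (SAP 7.2.5): d + 1.

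**Boundary.**

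| d | Study Day | TEAE by formula | TEAE by words | Excluded by 7.2.5 |
|---|---|---|---|---|
| 29 | 30 | yes | yes | no |
| 30 | 31 | no | yes | no |
| 31 | 32 | no | no | yes |

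The formula admits d = 0 to 29, which is 30 dates. The words admit d = 0 to 30, which is 31 dates. They differ at d = 30 alone. With dosing on 1 January, 30 January is in by both and 31 January is in by the words only. Grouping the formula as onset minus (dose + 1) ≤ 30 gives d ≤ 31, so that reading does not restore agreement.

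**How an onset at +30 could reach the data.** The last scheduled contact is at +5 to +10. Footnote (l) covers reports made up to 30 days after dosing, so by that route an onset at +30 must be reported the same day. Once recorded, it appears in the listings, because Protocol 13.1.4 and SAP 7.11.1 list all AEs. One such subject would move a TEAE count by 1 of 20 in a dose group (5 percentage points) or 1 of 40 overall (2.5 points).

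**Late SAEs, side by side.**

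| Place | Act governed | Relatedness condition | Time limit |
|---|---|---|---|
| Protocol 10.2.2 | report to sponsor after the collection period | yes | none |
| Appendix A footnote (l) | entry in database as a TEAE | none | reported within 30 days |
| Appendix B item 12 | notify sponsor of an SAE | none | within 24 hours |

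Protocol 10.2.2 says an SAE goes to the sponsor *if* related. It does not say *only if*, and it keeps nothing out of the database. Footnote (l) and Protocol 10.2.1.2 put the unrelated event in, and Appendix B gives a route to the sponsor.

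The number of report dates on which 10.2.2 and footnote (l) differ in wording depends on where the collection period ends:

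- Day 2 (d = 1): +2 to +30, 30 − 1 = 29 dates;
- contact at +5: +6 to +30, 30 − 5 = 25 dates;
- contact at +10: +11 to +30, 30 − 10 = 20 dates;
- collection taken to run to +30: none.

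These are calendar dates, not expected events. The documents give no expected SAE count.

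**The case for a change.** The best case for acting is that the contradiction sits inside a single sentence. The SAP does not say whether words or formula govern, SAP 7.2.5 sides with the words, and the repair is editorial. The phrase in Protocol 13.1.4 can be squared with the formula by counting the dosing day as day 1, but the phrases in SAP 7.11.1 and 7.2.5 cannot. On late SAEs, a site could follow 10.2.2 alone and never look at a footnote to the schedule. Spontaneous reports are also the main way that any late onset would arrive, so both ambiguities fall on the same few events.

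The arithmetic stands in full, and the mismatch is not a reading artefact. The consequence does not follow. An explicit inequality repeated identically in two documents is what a programmer codes. SAP 7.2.5 works in one direction: it removes late onsets from summaries and does not declare every earlier one a TEAE. Either boundary is defensible, so a correction would settle a convention and would not improve the safety assessment. Changing the formula in Protocol 13.1.4 as well would need prior IRB/IEC approval under Appendix B, item 5, so that route costs more than an edit to the text.

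On late SAEs, what stands is that the passages are worded unevenly and that the end of the collection period could be stated once. That is a matter of clarity. Both descriptions of the collection period provide for AEs to be gathered at the 5 to 10 day contact, so in substance they agree.

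**Conclusion.** No change is called for. The TEAE sentence holds a clerical off-by-one: the words end at dose date +30 and the formula at +29. It can reclassify only an onset on exactly +30. That onset lies at least 20 days after the last scheduled contact (30 − 10 = 20), and the event would be listed under either reading. Analysts can apply the formula that both documents share.

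The late-SAE passages differ in wording but are compatible when read together. Footnote (l) secures database entry without regard to relatedness, and Appendix B, item 12, secures notification of the sponsor.

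The conclusion rests on three assumptions: the shared formula is what is programmed, sites follow footnote (l) and Appendix B as well as 10.2.2, and late serious events are few among 40 healthy subjects given one dose. The documents give no rate with which to test the last. No group comparison is biased, since the same rules apply to both dose groups, and the PK endpoints are unaffected.

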7.11.2 Physical Examination

The physical examination findings will be presented in data listings.

7.11.3 Clinical Laboratory Evaluations

All laboratory test parameters will be displayed in individual subject data listings in both SI units and conventional (CV) units. For test results not in SI units, the conversion to SI units will be done in the derived analysis datasets using the known conversion factors. If necessary, SI units from the central laboratory may be converted to Takeda's preferred SI units in the derived analysis datasets. All summaries will be based on the values using these preferred SI units.

Clinical laboratory values (hematology, serum chemistry, and urinalysis) will be summarized (N, mean, SD, median, minimum, and maximum) by dose group using descriptive statistics for baseline, postdose, and change from baseline to postdose values. Only observations within 7 days of the last dose of study drug will be included in the summaries. No inferential statistics will be presented unless otherwise stated.

A table with predefined criteria for markedly abnormal values for laboratory variables ([Appendix A](#)) will be presented. If a subject has a MAV for a particular laboratory test, all visits for that subject for that parameter will be listed. The number and percentage of subjects with at least 1 postdose markedly abnormal laboratory test result will be summarized. The mapping of the subjects who meet the MAV criteria will be listed as a table. All observations, including ones at unscheduled visits, will be included in the MAV evaluation and summaries.

All clinical laboratory data will be displayed in data listing. Laboratory data outside of the normal reference range will be indicated in the listings. In addition, MAVs will be flagged. The listing will include site number, subject identifier, age, gender, treatment group, study visit, and sample collection date and time. MAV listings will be presented in the unit specified in the MAV criteria in [Appendix A](#).

7.11.4 Vital Signs

Vital signs will include weight, oral or axillary body temperature measurement, sitting blood pressure (after 5 minutes resting), respiration rate and pulse beats per minute (bpm). Only blood pressure and pulse will be taken on Check-in (Day -1) through Day 2.

Vital signs will be summarized (N, mean, SD, median, minimum, and maximum) for each dose group by presenting descriptive statistics for baseline, postdose, and change from baseline to postdose values.

Vital signs that meet predefined markedly abnormal criteria ([Appendix B](#)) will be presented. If a subject has a MAV for a particular vital sign, all visits for that subject for that vital sign will be listed. The number and percentage of subjects with at least 1 postdose markedly abnormal vital signs measurement will be summarized. The mapping of the subjects who meet the MAV criteria will be listed as a table. All observations, including ones at unscheduled visits, will be included in the MAV evaluation and summaries.

All vital sign data will be provided in the data listings. Vital sign MAVs will be flagged in the listings. The listing will include site number, subject identifier, age, gender, treatment group, study visit, and sample collection date and time.

7.11.5 12-Lead ECGs

ECG results will be interpreted using 1 of the following categories: within normal limits, abnormal but not clinically significant, or abnormal and clinically significant. Shift tables for ECG evaluation will be provided by dose groups. All ECG data will be listed in the data listings.

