7.1 Inclusion Criteria

Subject eligibility is determined according to the following criteria prior to entry into the study:

1. In the opinion of the investigator, the subject is capable of understanding and complying with protocol requirements.
2. The subject or, when applicable, the subject's legally acceptable representative signs and dates a written, informed consent form and any required privacy authorization prior to the initiation of any study procedures including requesting that a subject fast for any laboratory evaluations.
3. The subject is a healthy adult man or woman of Chinese descent.
4. The subject is aged 18 to 45 years, inclusive, at the time of informed consent and study medication dose.
5. The subject weighs at least 50 kg and has a body mass index (BMI) from 19.0 to 26.0 kg/m², inclusive at Screening Visit.
6. A man who is nonsterilized* and sexually active with a woman of childbearing potential* agrees to use adequate contraception* from signing of informed consent throughout the duration of the study and for 30 days after last dose of study drug.
7. If a woman of childbearing potential* is sexually active with a nonsterilized* man, she agrees to routinely use adequate contraception* from signing of informed consent throughout the duration of the study and for 30 days following the last dose of study drug. Women of childbearing potential* must have a negative pregnancy test at Screening and Check-in (Day -1 of Period 1) and they must not be nursing.

*Definitions and acceptable methods of contraception are defined in Section [9.1.9](#) Contraception and Pregnancy Avoidance Procedure and reporting responsibilities are defined in Section [9.1.10](#) Pregnancy.

8. Subject has clinical chemistry, hematology, and complete urinalysis (fasted for at least 8 hours) at the Screening Visit and Check-in (Day -1) results within the reference range for the testing laboratory unless the out of range results are deemed not clinically significant by both the investigator and Medical Monitor.

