11. Subject has taken any excluded medication, supplements, or food products during the time periods listed in the Excluded Medications, Supplements, and Dietary Products [Table 7.a](#) listed in Section [7.3](#).
12. If a woman is pregnant or lactating or intending to become pregnant before, during, or within 30 days after participating in this study; or is intending to donate ova during such time period.
13. If a man intends to donate sperm during the course of this study or for 30 days thereafter.
14. Subject has a history of cancer, except basal cell carcinoma which has been in remission for at least 5 years prior to Day 1.

15. Subject has a positive test result for hepatitis B surface antigen (HBsAg), hepatitis C virus (HCV) antibody, or human immunodeficiency virus (HIV) antibody at Screening.
16. Subject has used nicotine-containing products (including but not limited to cigarettes, pipes, cigars, chewing tobacco, nicotine patch or nicotine gum) within 28 days prior to Check-in (Day -1) or is unwilling to abstain from these products for the duration of the study.
17. The subject has poor peripheral venous access.
18. Subject has donated blood products (such as plasma), whole blood or had a significant blood loss (450 mL) within 56 days of Day 1.
19. Subject has a Screening or Check-in (Day -1) abnormal (clinically significant) ECG. Entry of any subject with an abnormal (not clinically significant) ECG must be approved, and documented by signature by both the principal investigator and the medical monitor.
20. Subject has abnormal Screening or Check-in (Day -1) laboratory values that suggest a clinically significant underlying disease or subject with the following lab abnormalities: creatinine >1.5 mg/dL, alanine aminotransferase (ALT) and/or aspartate aminotransferase (AST) >2.5x the upper limits of normal (ULN), or total bilirubin >2.0 mg/dL.

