7.2.4 Definition of Baseline and Change from Baseline

Baseline is defined as the last non-missing measurement prior to first dose of study drug.

CONFIDENTIAL

The change from baseline will be calculated by subtracting the baseline values from the individual post-baseline values. If either the baseline or post-baseline value is missing, the change from baseline is set to missing as well.

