Appendix A Criteria for Identification of Markedly Abnormal Laboratory Values

Hematology—Criteria for Markedly Abnormal Values

Parameter	Low Abnormal	High Abnormal
Hemoglobin	<0.8 × LLN,	>1.2 × ULN
Hematocrit	<0.8 × LLN,	>1.2 × ULN
RBC count	<0.8 × LLN,	>1.2 × ULN
WBC count	<0.5 × LLN	>1.5 × ULN
Platelet count	<75 x 10 ³ /µL	>600 x 10 ³ /µL

RBC=red blood cell, WBC=white blood cell.

Chemistry—Criteria for Markedly Abnormal Values

Parameter	Low Abnormal	High Abnormal
ALT	--	>3x ULN
AST	--	>3x ULN
GGT	--	>3x ULN
Alkaline phosphatase	--	>3x ULN
Total bilirubin	--	>2.0 mg/dL
Albumin	<2.5 g/dL	--
Total protein	<0.8x LLN	>1.2x ULN
Creatinine		>2.0 mg/dL
Blood Urea Nitrogen	--	>30 mg/dl
Sodium	<130 mEq/L	>150 mEq/L
Potassium	<3.0 mEq/L	>6.0 mEq/L
CPK	--	>5x ULN

ALT=alanine aminotransferase, AST=aspartate aminotransferase, GGT=γ-glutamyl transferase, CPK=creatinine phosphokinase, LLN=lower limit of normal, ULN=upper limit of normal.

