Appendix B Criteria for Markedly Abnormal Values for Vital Signs

Parameter	Unit	Lower Criteria	Upper Criteria
Pulse	bpm	<50	>120
Systolic blood pressure	mm Hg	<85	>180
Diastolic blood pressure	mm Hg	<50	>110
Body temperature (axillary)	°C	<35.6	>37.7

TAK-390MR_106 Statistical Analysis Plan

ELECTRONIC SIGNATURES

Signed by	Meaning of Signature	Server Date (dd-MMM-yyyy HH:mm 'UTC')
Personally Protected Data	Biostatistics Approval	22-Mar-2018 16:11 UTC
	Clinical Operations Approval	22-Mar-2018 16:37 UTC
	Pharmacovigilance Approval	23-Mar-2018 00:34 UTC
	Clinical Science Approval	23-Mar-2018 09:59 UTC

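### The count of markedly abnormal pulse and blood pressure ignores baseline, so subjects already beyond a limit before dosing are counted as postdose abnormalities (minor)

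*SAP*

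**What the plan says.** For vital signs, SAP 7.11.4 states: "The number and percentage of subjects with at least 1 postdose markedly abnormal vital signs measurement will be summarized". It adds: "All observations, including ones at unscheduled visits, will be included in the MAV evaluation and summaries". SAP 7.11.3 has the same rule for laboratory tests: "The number and percentage of subjects with at least 1 postdose markedly abnormal laboratory test result will be summarized". Neither section refers to the baseline value when defining who is counted.

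The limits are in SAP Appendix B, "Criteria for Markedly Abnormal Values for Vital Signs": pulse below 50 or above 120 bpm, systolic pressure below 85 or above 180 mm Hg, diastolic pressure below 50 or above 110 mm Hg.

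SAP 7.2.4 does define a baseline: "Baseline is defined as the last non-missing measurement prior to first dose of study drug". It is used for the change-from-baseline summaries. The only display that cross-classifies a subject's baseline and postdose status is the ECG shift table in SAP 7.11.5.

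Protocol 7.1 and 7.2 require a healthy adult without serious cardiovascular disease, but give no number for pulse or blood pressure.

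**The concern.** A table of postdose abnormalities is normally read as showing what appeared after dosing. Here a person with a resting pulse of, say, 48 bpm at Screening, Check-in, the morning of Day 1 and Day 2 is eligible on the numbers and is counted, although nothing changed.

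The study has two active dose groups of 20 and no placebo, so the table has no background rate to be read against. Each subject's own predose value is the only available reference, and the count does not use it. The reported percentage then mixes long-standing values with new ones, and a difference between the 30 mg and 60 mg columns could reflect who happened to be enrolled in each group.

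**Working it through.** The plan gives no expected rate of markedly abnormal values (MAVs), so there is no figure to reproduce. The check compares the limits and then gauges the possible size.

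**1. Entry limits against vital-sign MAV limits**

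| Measure | Numeric entry limit (Protocol 7.1, 7.2) | Low MAV limit (SAP Appendix B) | Can baseline already meet it? |
|---|---|---|---|
| Pulse | none | <50 bpm | yes |
| Systolic pressure | none | <85 mm Hg | yes |
| Diastolic pressure | none | <50 mm Hg | yes |

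**2. Weight of one subject.** With 20 per group (SAP 4.3), one subject is 1/20 = 5 percentage points. This assumes the count is shown by dose group, like the other vital-sign summaries in that section.

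**3. Chance of at least one counted subject with no drug effect.** If a share p of subjects reads beyond a limit after dosing regardless of drug, the chance in a group of 20 is 1 − (1 − p)^20:

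- p = 1%: 18%
- p = 2.5%: 40%
- p = 5%: 64%
- p = 10%: 88%

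The documents do not give p.

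**4. How many counted subjects were already beyond the limit.** This was simulated with no drug effect, using 1,000,000 subjects per scenario. Each reading is the subject's own level (normal, between-subject SD) plus independent error (normal, within-subject SD). There is one baseline reading and two postdose readings; two is how I read Protocol Appendix A, footnote f (8 hours postdose and the morning of Day 2). A subject is counted if either postdose reading is below 50, and is classed as already met if the baseline reading is also below 50. All means and SDs are assumptions.

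| Criterion | Mean / between SD / within SD | Expected count per 40 | Of these, not met at baseline | Share already met |
|---|---|---|---|---|
| Pulse <50 | 70 / 6 / 4 | 0.20 | 0.16 | 18% |
| Pulse <50 | 65 / 8 / 5 | 3.53 | 2.22 | 37% |
| Pulse <50 | 60 / 8 / 5 | 8.50 | 4.47 | 47% |
| Diastolic <50 | 70 / 6 / 4 | 0.20 | 0.16 | 17% |
| Diastolic <50 | 66 / 7 / 5 | 2.12 | 1.54 | 28% |
| Diastolic <50 | 62 / 7 / 5 | 5.16 | 3.28 | 36% |

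Shares come from unrounded values. For each criterion the first and last rows are the extremes of the scenarios run. By subtraction, subjects already beyond the limit number 0.04 to 4.03 per 40 for pulse and 0.04 to 1.88 for diastolic pressure. Systolic pressure was not modelled.

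**5. Do the laboratory tests share the problem?** Exclusion 20 in Protocol 7.2 applies at Screening and Check-in, and Check-in is the last scheduled predose laboratory visit.

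| Test | Highest value admitted | MAV limit (SAP Appendix A) | Gap |
|---|---|---|---|
| Total bilirubin | 2.0 mg/dL | >2.0 mg/dL | 0 |
| Creatinine | 1.5 mg/dL | >2.0 mg/dL | 0.5 mg/dL |
| ALT, AST | 2.5× ULN | >3× ULN | 0.5× ULN |

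An eligible subject cannot meet any of these MAV limits at Check-in, so a baseline split reclassifies nobody for these tests. Tests without a numeric entry limit, such as GGT, are governed by inclusion 8, which admits out-of-range values only under a condition: "unless the out of range results are deemed not clinically significant by both the investigator and Medical Monitor". For those tests a baseline MAV is possible but less likely.

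**The case against.** The strongest reply is that the information is already there. For any subject with a MAV the SAP lists every visit for that measure and flags the values, and it summarizes baseline, postdose and change by dose group. With 40 subjects and few postdose readings, a reader can check each case. Protocol 13.1.4 asks only that such values be presented, and no decision or test depends on the count. General health requirements, and dual sign-off of ECGs that are abnormal but not clinically significant, also make extreme resting values less likely. All of this stands and keeps the point minor. It does not repair the summary percentage, which still mixes two kinds of subject, and a group mean change cannot show whether a given MAV is new.

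A second reply is that the size rests on assumptions and that most counted subjects would remain after the split. That is also right: in every scenario run, more than half of those counted did not meet the criterion at baseline and crossed the limit through ordinary variation.

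A reader might infer that bilirubin shows the same fault, because the exclusion ("or total bilirubin >2.0 mg/dL") and the MAV limit ("Total bilirubin -- >2.0 mg/dL") coincide. The documents do not support this. A value above the limit at Check-in excludes the subject, so what remains is fluctuation across a shared limit, which a baseline split does not address. The ALT and AST limits leave a gap and give no support either. Nor does temperature lack a predose value: it is taken at Screening (Protocol Appendix A, footnote f), which counts as baseline under SAP 7.2.4.

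**Conclusion.** The concern holds for pulse and blood pressure. The count takes no account of baseline, the entry criteria allow a baseline value beyond the Appendix B limits, and there is no control group. Each subject affected adds 5 percentage points to a 20-subject column. The number affected cannot be derived from the documents; under the assumptions above it runs from almost none to about 4 of 40 for pulse and about 2 of 40 for diastolic pressure.

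A reader might go further and conclude that the safety objective cannot be addressed, or that subjects new after dosing represent a drug effect. Neither follows. The adverse event tables, the change-from-baseline summaries and the listings also serve that objective, and the new-postdose row will still contain chance crossings. Severity is minor: this is one descriptive table for a secondary objective.

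**What to change.** In SAP 7.11.4, keep the total row for subjects with at least one postdose MAV and add two rows beneath it for each measure and direction:

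- new postdose: criterion not met at the SAP 7.2.4 baseline;
- already met at baseline.

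Use the same layout in SAP 7.11.3 for consistency, accepting that it will move nobody for bilirubin, creatinine, ALT or AST. Keep the all-visits listing, because the split alone does not show worsening in a subject who was already abnormal, and because one baseline reading can miss a subject who was beyond the limit at Screening or Check-in.

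The cost is one sentence in each section, a baseline flag in the derived dataset and two extra table rows. No new data are needed, the total count is not lost, and no entry criterion or MAV limit changes.
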